**FLOW increases access.** During implementation, 1,566 patients in participating clinics were identified as potentially meeting criteria for transition and 411 unique recovered MH patients transitioned from MH to PC. Of those, only nine (2%) returned to MH for care after the transition. The patients transitioned represented 16% of all unique patients (n=2,504) treated in the clinics implementing FLOW, suggesting that FLOW had a significant impact on workflow and access. After our team left the site, they continued using FLOW to transition a further 205 patients and independently implemented the program at a nearby CBOC. Initial data suggests that FLOW increased access and timeliness for new patients to obtain a SMH appointment (Figure 2). This increase was not due to an increase in mental health staffing, as MH FTEE per 1000 patients decreased during the initial implementation of FLOW in 2017. At 12-months post-implementation, qualitative data indicated that providers felt FLOW increased access for patients, increased communication among providers, and for SMH providers, decreased their own stress related to workload, although they reported that sometimes

the transition process was not as smooth as they would have liked. Qualitative patient interviews suggested that many patients felt ready for transition, although some were surprised by being asked to transition and recommended that patients be prepared earlier, which is incorporated in FLOW.

**Figure 2.** % patients who received a SMH appointment within 7 days of the preferred date before and after implementation of FLOW at site 1, compared with MH FTEE.

**Other sites.** FLOW is being piloted at 3 other sites in VISNs 16 and 17. Initial data suggest substantial variability in uptake of FLOW. Sites 2 and 3 have transitioned 7 and 8% of unique MH patients. At site 4, implementation is paused due to inability to enact project tasks. Substantial variation also exists in provider adoption (100% and 92% at sites 1 and 2, 33% at site 3). Sites differ significantly in readiness to implement and more work is needed to understand key barriers and facilitators to refine implementation methods.

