**Power analysis.** Power calculations were conducted for the reach and effectiveness outcomes using the Steppedwedge command in Stata Version 14. Although between 7 and 9 sites will participate, power calculations were estimated conservatively, assuming only 6 facilities (clusters) with 2 randomized into each of the 3 steps of the predominately open cohort (i.e., different patients at different timepoints) complete design. Calculations assume a two-tailed alpha of 0.05. VISN 19 leadership reports that few patients are currently being transitioned from MH to PC. Transition rates are <1% of patients in facilities who do not receive the FLOW intervention and between 1-16% of patients in facilities who do receive the FLOW intervention. Given an average of 1000 patients per quarter per facility based upon the Clinic Practice Manager data for VISN 19, a sample size of 6 clusters (24,000 patients in total) achieves 80% power to detect a difference in transition rates from 1% at baseline to 1.65% upon receiving FLOW. Power is >99% to detect a two-fold increase in patients who transition from SMH to PC. Reach, effectiveness, and most maintenance outcomes are binary variables at the patient level (e.g., whether one was transitioned to PC). These outcomes represent an open cohort trial, as different patients will be included at each timepoint within a given site. Adoption outcomes are both binary (e.g., whether a provider engaged in the FLOW process for at least 3 patients) and continuous (e.g., % of patients engaged in FLOW for each provider) at the provider level. These outcomes represent a closed cohort trial, as the same providers will be included at each timepoint. Adequate effectiveness will be declared if at least 90% of transitioned patients successfully transition without return to SMH in the 1 year follow-up period. Given a very conservative estimation that 4% of SMH patients transition from SMH to PC, an average of 40 patients per quarter per facility (4% of 1000 = 40), a sample size of 6 clusters (960 transitions in total) will allow for 80% power to detect a difference in the percentage of patients who successfully transitioned to primary care from 76.50% to 90% upon receiving FLOW.

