Downstream effectiveness, or impact upon access, will be measured as increase in appointments within 7 days of requested date from pre-implementation to post-implementation. Data extracted from the Clinic Practice Manager suggests a fairly high baseline rate of clinic patients receive appointments within 7 days of desired date in VISN 19 (~75 to 80%). Given an average of 1000 patients per quarter per facility, a sample size of 6 clusters (24,000 patients in total) achieves 80% power to detect a difference in the percentage of patients receiving appointments within 7 days of desired date from 80% at baseline to 83% upon receiving FLOW. Power calculations are consistent with ICC values of .10, .15, .20, and .25 and would be similar to what is described above for the maintenance phase.

**Quantitative data analysis.** We will begin by describing the number of participants, providers, and sites (clusters) who were randomly assigned to each sequence and the numbers included at each quarter. Intervention conditions will initially be compared using generalized linear mixed models (HGLMs) for binary outcomes and hierarchical linear mixed models for continuous outcomes. Each model will include intervention (yes/no) and quarter as fixed predictors and models for reach, effectiveness (except for gain in provider hours), and maintenance will also include the value of the outcome during the baseline quarter as a fixed predictor. Site will be included in all models as a random effect. As we expect the intervention effect may be delayed and reach its peak at the end of the implementation period or that the effect may plateau or even decay during the maintenance period, we will also conduct a set of models where the treatment by time interaction is included as a fixed effect. Furthermore, given the sequences have different lengths of maintenance we will be able to examine whether maintenance varies with time since removal of external facilitator.

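### The reach model allows a single FLOW effect for all sites, so its confidence interval for the average effect is likely too narrow

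*Combined protocol and SAP*

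**What the plan says.** The model is set out under C. Methods, Quantitative data analysis. "Each model will include intervention (yes/no) and quarter as fixed predictors", and "Site will be included in all models as a random effect". The reach model also adjusts for the outcome in the baseline quarter. A further set of models relaxes the constant effect over time: "we will also conduct a set of models where the treatment by time interaction is included as a fixed effect". That term is fixed too, so it lets the effect change over time but in the same way at every site. No site-by-intervention term, robust variance or small-cluster method is named.

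On how sites respond, Background and Significance reports for site 1: "The patients transitioned represented 16% of all unique patients (n=2,504) treated in the clinics implementing FLOW". For the others: "Sites 2 and 3 have transitioned 7 and 8% of unique MH patients" and "At site 4, implementation is paused due to inability to enact project tasks". The Power analysis plans for transition in "between 1-16% of patients in facilities who do receive the FLOW intervention". Site differences are studied under Aim 2 by comparative case study and QCA.

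**The concern.** With a fixed intervention term and a site intercept, the model has no place for a site whose response to FLOW is above or below average. Such a departure lasts through all of that site's FLOW quarters. The intercept, the quarter terms and the baseline value do not absorb it. The model then measures precision largely by the number of patients (about 1000 per site-quarter), whereas precision about the average effect is limited by having 7 to 9 sites.

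At stake is the interval around the size of the FLOW effect on reach. The plan says the evaluation should inform a possible national rollout, where the uncertainty in the average effect, and the spread around it, are what a reader will want.

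**Working it through.** **1. The plan's own figure assumes a common effect.** Inputs from Power analysis: 6 sites, 2 per step, 3 steps (4 periods), 1000 patients per site-quarter, 1% versus 1.65%, "Calculations assume a two-tailed alpha of 0.05"; ICC 0.10 is the lowest of the values listed. The Hussey-Hughes variance is

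Var = Iσ²(σ² + Tτ²) / [(IU − W)σ² + (U² + ITU − TW − IV)τ²].

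- Total variance 0.01 × 0.99 = 0.0099, so σ² = 0.0099 × 0.9/1000 = 8.91×10⁻⁶ and τ² = 0.00099.
- I = 6, T = 4, U = 12, W = 56, V = 28.
- Numerator 2.122×10⁻⁷; denominator 16 × 8.91×10⁻⁶ + 40 × 0.00099 = 0.03974; SE = 0.00231.
- Power = Φ(0.0065/0.00231 − 1.96) = 80.3%, against 80% stated.

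Adding a between-site SD of the risk difference of 0.325 points (half the effect) raises the SE to 0.00267 and lowers power to 68%. With 0.65 points it is 0.00352 and 45%. These SDs are illustrations; the documents give none.

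**2. What the pilot suggests about spread.** The logits of 16%, 7% and 8% are −1.658, −2.587 and −2.442, with SD 0.50. If the paused site is set at 1% (an assumption; no rate is given), the SD is 1.25. With three values, the nominal 95% interval for an SD of 0.50 runs from 0.50√(2/7.378) = 0.26 to 0.50√(2/0.0506) = 3.1.

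**3. A hand check.** For the mean effect over sites like these, the SE cannot fall below SD/√sites, however many patients there are. For 7 sites this is 0.25/√7 = 0.09, 0.5/√7 = 0.19 and 1.0/√7 = 0.38. The common-effect model reports about 0.14 whatever the spread.

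**4. Simulation of the planned model.** Seven sites (2/3/2) and 12 quarters from Table 1; 1000 patients per site-quarter; binomial data with site-varying log odds ratios. The fit was logistic with site, quarter and one intervention effect. Sites were fitted as fixed, which is close to a random intercept at this cell size and absorbs any site-level baseline value. The 6% FLOW rate is an assumption within the planning range. Coverage of the nominal 95% interval, as ranges over repeat simulations:

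| Between-site SD | 1% to 6% per quarter | A quarter of those rates (0.25% to 1.5%) |
|---|---|---|
| 0.25 | 84-89% | 94-95% |
| 0.5 | 61-65% | 78-85% |
| 1.0 | 31-35% | 58-61% |

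With no spread, coverage is about 93-95%. At SD 0.5 on the higher scale the model SE is 0.14, while the estimate's true SD is about 0.30. At SD 1.0 the estimate also overstates the mean log odds ratio by about 0.35. At 300 replicates the Monte Carlo standard error near 65% is √(0.65 × 0.35/300) = 2.8 points.

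**5. The alternative.** A leave-one-site-out jackknife SE with t on 5 df gave coverage of about 88-98%, with the low end at SD 1.0.

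**The case against.** The strongest reply is that the pilot does not estimate how much the effect varies. Site 1 had completed implementation with 12-month follow-up, while sites 2 and 3 were reporting early data, so part of the gap may be elapsed time. The denominators may differ. The figures are rates under FLOW with no site baselines, so they are not log odds ratios. Sites 2 and 3 differ by only 0.14 on the logit scale, so site 1 drives the SD. All of this stands, and it is why the SD is treated as an assumption with a range.

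The time scale is also open. The pilot percentages accumulate over implementation, whereas the Power analysis applies percentages to patients per quarter. At lower quarterly rates the shortfall shrinks, and at SD 0.25 it almost vanishes.

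The target may be only the enrolled sites. Coverage at SD 0.5 is then about 78% on the higher scale and 89% on the lower, so the shortfall is smaller but not absent.

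Aim 2 does examine site differences, but QCA sorts sites into high and low success and does not alter the interval.

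A reader might go further and infer that the interval is far too narrow, that the test of FLOW is invalid, or that the access result has the same fault. The documents support none of these. The spread in the new sites is unknown. If FLOW does nothing at any site there is no spread to ignore, so that test keeps its error rate from this source. In simulations at 1% to 6%, the interval excluded zero every time even at SD 1.0. No site-level spread is given for access.

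**Conclusion.** The point holds for the reach interval. As written, the model imposes one effect on sites that the plan itself expects to respond differently, and the interval for the average effect is likely too narrow. The shortfall ranges from negligible (SD 0.25, lower quarterly rates) to severe (SD 1.0, 1% to 6% per quarter).

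This rests on four assumptions: site as a random effect means an intercept only; the between-site SD lies somewhere in 0.25 to 1.0; the quarterly rates lie on one of the two scales shown; and the target is the average over sites like those enrolled. It concerns the interval and the size of the average effect, not whether FLOW has any effect.

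**What to change.** Pre-specify for the reach model that the interval is the estimate ± t(0.975, S − 2) × SE, where S is the number of sites and SE = √[(S − 1)/S × Σ(θ₍₋ᵢ₎ − θ̄)²] from refitting with each site left out in turn. Fit a random site-by-intervention effect as a supporting analysis where it converges. It should not be the main basis: its coverage was not checked here, and with 7 sites it may not converge. Report each site's own estimate and the between-site SD beside the average. Apply the same to access as a precaution.

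The cost is a little more code and wider intervals; the design and data collection are unchanged. With 7 sites and no spread, the half-width on the log-odds scale grows from 1.96 × 0.14 = 0.27 to 2.57 × 0.14 = 0.36. At SD 0.5 it would be about 2.57 × 0.30 = 0.77.
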